9.3.4. Infusion Reactions

Infusion reactions are defined as any AE that occurs during the infusion or within 2 hours after the infusion is completed. All infusion reactions must be reported as AEs (defined in Section 9.4.1) and graded using the grading scales as instructed in Section 9.5.1.

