9.4.3. Other Events that Require Accelerated Reporting to Sponsor

The following events also require reporting to the sponsor (or designee) within 24 hours of learning of the event:

Symptomatic Overdose of Study Drug: Accidental or intentional overdose of at least 2 times the intended dose of study drug within the intended therapeutic window, if associated with an AE.

Pregnancy: Although pregnancy is not considered an AE, it is the responsibility of the investigator to report to the sponsor (or designee), within 24 hours of identification, any pregnancy occurring in a female or female partner of a male, during the study or within 24 weeks of the last dose of study drug. Any complication of pregnancy affecting a female study patient or female partner of a male study patient, and/or fetus and/or newborn that meets the SAE criteria must be reported as an SAE. Outcome for all pregnancies should be reported to the sponsor.

Adverse Events of Special Interest: All AESIs, serious and nonserious, must be reported within 24 hours of identification using the same reporting process as for SAE reporting, per Section 9.4.2.

Adverse events of special interest (serious or non-serious) for evinacumab include the following:

- Anaphylactic reactions
- Allergic reactions and/or local injection site reactions that require consultation with another physician for further evaluation or requiring medical treatment
- Increase in ALT or AST: ≥ 3 x ULN (if baseline <ULN), or ≥ 2 times the baseline value (if baseline \geq ULN)
- Pregnancy
- Symptomatic overdose with investigational medicinal product
- Neurocognitive events
- New onset of diabetes (see definition below)
- Pancreatitis

Adverse events of special interest for alirocumab include the following:

- Increase in ALT: ALT ≥ 3 x ULN (if baseline ALT <ULN), or ALT ≥ 2 times the baseline value (if baseline ALT \geq ULN)
- Allergic events and/or local injection site reactions that require consultation with another physician for further evaluation

- Pregnancy
- Symptomatic overdose with investigational medicinal product
- Neurologic events that require additional examinations/procedures and/or referral to a specialist
- Neurocognitive events
- Cataracts
- New onset of diabetes: The definition of new onset of diabetes (NOD) will be the following:
 - Type 1 or type 2 diabetes TEAE (grouping of Medical Dictionary for Regulatory Activities [MedDRA®] terms will be specified in the SAP)and/or

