10.4.4.1. Adverse Events

All AEs reported in this study will be coded using the currently available version of the Medical Dictionary for Regulatory Activities (MedDRA®). The verbatim text, the preferred term (PT), and the system organ class (SOC) will be provided in patient listings.

Definitions

For safety variables, the following observation periods are defined:

- The pretreatment period is defined from the day the ICF is signed to the day before the first dose of double-blind study treatment.
- The double-blind TEAE observation period is defined from the day of the first dose of double-blind study treatment to the day of the last dose of double-blind study treatment + 168 days (24 weeks) (residual effect of treatment for IV dose regimen is expected until 24 weeks after the last dose of study drug) for those patients not proceeding into the OLTP, or up to the day before the first dose of open-label study treatment administration for those patients proceeding into the OLTP.
- The open-label TEAE observation period is defined from the day of the first open-label study treatment administration to the day of the last open-label study treatment administration + 168 days.
- The post-treatment observation period is defined as the time from the day after the end of the respective TEAE periods to the last study visit.

Double-blind TEAEs are defined as those events that developed, worsened, or became serious during the double-blind TEAE period. Open-label TEAEs are defined as those events that developed, worsened, or became serious during the open-label TEAE period.

Analysis

Adverse event incidence tables will present data by SOC sorted alphabetically and PT sorted by decreasing frequency, and summarize the number (n) and percentage (%) of patients experiencing an AE. Multiple occurrences of the same event in the same patient will be counted only once in the tables. Data conventions for missing or partial AE dates will be addressed in the SAP. The denominator for computation of percentages is the respective SAF populations (ie, double-blind SAF or open-label SAF) within each treatment group.

Summaries of TEAEs incidences will include:

- All TEAEs (and patient listing)
- All treatment-emergent SAEs, including patient deaths (and patient listing)
- All TEAEs of special interest for alirocumab treatment (ie, increase in ALT, etc)
- All TEAEs of special interest for evinacumab treatment (anaphylactic reaction, etc)

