9.4.3. Other Events that Require Accelerated Reporting to Sponsor

The following events also require reporting to the sponsor (or designee) within 24 hours of learning of the event:

Symptomatic Overdose of Study Drug: Accidental or intentional overdose of at least 2 times the intended dose of study drug within the intended therapeutic window, if associated with an AE.

Pregnancy: Although pregnancy is not considered an AE, it is the responsibility of the investigator to report to the sponsor (or designee), within 24 hours of identification, any pregnancy occurring in a female or female partner of a male, during the study or within 24 weeks of the last dose of study drug. Any complication of pregnancy affecting a female study patient or female partner of a male study patient, and/or fetus and/or newborn that meets the SAE criteria must be reported as an SAE. Outcome for all pregnancies should be reported to the sponsor.

Adverse Events of Special Interest: All AESIs, serious and nonserious, must be reported within 24 hours of identification using the same reporting process as for SAE reporting, per Section 9.4.2.

Adverse events of special interest (serious or non-serious) for evinacumab include the following:

- Anaphylactic reactions
- Allergic reactions and/or local injection site reactions that require consultation with another physician for further evaluation or requiring medical treatment
- Increase in ALT or AST: ≥ 3 x ULN (if baseline <ULN), or ≥ 2 times the baseline value (if baseline \geq ULN)
- Pregnancy
- Symptomatic overdose with investigational medicinal product
- Neurocognitive events
- New onset of diabetes (see definition below)
- Pancreatitis

Adverse events of special interest for alirocumab include the following:

- Increase in ALT: ALT ≥ 3 x ULN (if baseline ALT <ULN), or ALT ≥ 2 times the baseline value (if baseline ALT \geq ULN)
 - Allergic events and/or local injection site reactions that require consultation with another physician for further evaluation
 - Pregnancy
 - Symptomatic overdose with investigational medicinal product
 - Neurologic events that require additional examinations/procedures and/or referral to a specialist
 - Neurocognitive events
 - Cataracts
 - New onset of diabetes: The definition of new onset of diabetes (NOD) will be the following:
 - Type 1 or type 2 diabetes TEAE (grouping of Medical Dictionary for Regulatory Activities [MedDRA®] terms will be specified in the SAP)
- and/or

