4.8.1.2. Adverse Events of Special Interest

Adverse events of special interest (AESI) are AEs (serious or non-serious) required to be monitored, documented, and managed in a pre-specified manner. AESIs will be recorded on the adverse event e-CRF using dedicated tick boxes, and/or identified using standard MedDRA queries (SMQ), company MedDRA queries (CMQ), and/or applicable laboratory assessments. Appendix 10.3 contains the definitions used to identify AESIs:

The AESIs include:

- Anaphylactic reactions (e-CRF)
- General allergic events (SMQ)
- Infusion reactions (e-CRF)
- Hepatic Disorder (SMQ, lab data)
- Pregnancy (e-CRF)
- Symptomatic overdose with investigational medicinal product (e-CRF)
- Neurocognitive events (CMQ)
- Neurologic events (e-CRF)
- New onset of diabetes (NOD) (lab data, HLT, concomitant medications) for patients without diabetes mellitus at baseline
- Diabetic complication (CMQ, concomitant medications) for patients with diabetes mellitus at baseline
- Pancreatitis (e-CRF)

- Cataracts (MedDRA HLT)
- Immune complex diseases (SMQ)
- Muscle events/CK elevation (MedDRA SOC, SMQ, lab data)

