10.3. List of AESIs with Data Sources and Definitions of SMQ/CMQ

Table 3: Summary of AESIs and the Methods of Data Collections and Derivations

AESI	Using an e-CRF specific tick box on AE page	Using Standard MedDRA Query (SMQ)/company MedDRA Query (CMQ) or lab data
Anaphylactic reactions	Yes	No
General allergic events	No	SMQ “hypersensitivity” (broad and narrow) excluding the following preferred terms linked to local injection site reactions (“infusion site dermatitis”, “infusion site hypersensitivity”, “infusion site rash”, “infusion site urticaria”, “injection site dermatitis”, “injection site hypersensitivity”, “injection site rash”, “injection site urticaria”, “injection site vasculitis”) plus “idiopathic angioedema”
Infusion reactions	Yes	No

Hepatic Disorders	No	
 • SMQ Drug-related hepatic disorder • Potentially clinically significant value (PCSV) in Appendix 10.4 Hy's law eDISH plot,
Pregnancy	Yes	No
Symptomatic overdose with investigational medicinal product	Yes	No
Neurocognitive events	No	
 • CMQ for neurocognitive events as defined based on Regulatory Agency request for another lipid lowering program (See Table 4 in Appendix 10.3 for the list of terms)
Neurologic events	Yes	No

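### The SAP has no AESI class for the local site reactions that Protocol 9.4.3 lists as AESIs, and removes nine site terms from its allergic class without reassigning them

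*SAP*

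**What the plan says.** The AESI lists are in Protocol 9.4.3, worded alike in the adult version and in the version that admits patients from 12 years.

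- For evinacumab the list includes "Allergic reactions and/or local injection site reactions that require consultation with another physician for further evaluation or requiring medical treatment".
- For alirocumab it includes "Allergic events and/or local injection site reactions that require consultation with another physician for further evaluation".

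Protocol 10.4.4.1 then plans incidence summaries of the special-interest events for each of the two drugs.

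SAP 4.8.1.2 gives its own list of AESIs, and Appendix 10.3, Table 3 states how each is found. The general allergic class is the hypersensitivity standardised MedDRA query (SMQ), broad and narrow, with idiopathic angioedema added, and "excluding the following preferred terms linked to local injection site reactions". Infusion reactions and anaphylactic reactions are each found by a tick box on the adverse event page. SAP 5.8.2 tabulates the AESIs that are listed in 4.8.1.2.

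The SAP does not define an infusion reaction. Protocol 9.3.4 does: "Infusion reactions are defined as any AE that occurs during the infusion or within 2 hours after the infusion is completed".

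**The concern.** Taking local site terms out of a general allergic class is sensible when a separate local-reaction class receives them. Table 3 gives that reason for the exclusion, but this SAP has no such class. The terms leave one class and enter none.

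If the SAP is followed exactly, an event type that the protocol singles out for 24-hour reporting has no place of its own in the AESI tables. The gap concerns a monoclonal antibody for which Protocol 3.2.3 names systemic hypersensitivity and immunogenicity as potential risks. Some patients also inject alirocumab, and the same section says that the safety of that combination will be watched carefully. A reader who looks for site reactions in the AESI tables would not find them there, and would not be told why.

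**Working it through.** No power, sample size or error-rate figure is involved. The check is to compare the lists and trace where an event can be counted.

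1. **Count the excluded terms (SAP Table 3).** Infusion site: dermatitis, hypersensitivity, rash, urticaria = 4. Injection site: the same four plus vasculitis = 5. Total 4 + 5 = 9.

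2. **Count the SAP classes (4.8.1.2).** Anaphylactic, general allergic, infusion reactions, hepatic, pregnancy, symptomatic overdose, neurocognitive, neurologic, new-onset diabetes, diabetic complication, pancreatitis, cataracts, immune complex diseases, muscle events = 14. Classes for local site reactions: 0.

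3. **Check the other protocol AESIs.** Anaphylaxis, allergic reactions, ALT/AST increases, pregnancy, overdose, neurologic and neurocognitive events, diabetes, pancreatitis and cataracts each have a counterpart in the SAP. Local site reactions are the only component without one.

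4. **Trace an event.** Take an infusion-site urticaria that starts the day after dosing and is referred to another physician. It meets the evinacumab criterion in Protocol 9.4.3, if that wording is read to cover infusion sites. The SAP reads it that way, because Table 3 groups the infusion-site terms with local injection site reactions.
   - General allergic: removed by its preferred term.
   - Infusion reactions: outside the 2-hour limit in Protocol 9.3.4.
   - Anaphylactic: only if it is part of an anaphylactic reaction and is ticked as one.
   - Immune complex diseases: built from the narrow queries for lupus, vasculitis and Guillain-Barré syndrome. The only excluded term that could plausibly enter is injection site vasculitis. The documents do not list query contents, so this stays open for 1 of the 9 terms.
   - The other 14 − 4 = 10 classes concern unrelated events.

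   The event enters no AESI table.

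5. **SC alirocumab.** Patients entering from R727-CL-1628 inject every 2 weeks, while infusions are every 4 weeks. If both schedules are kept, each 4-week cycle has 2 injections and 1 infusion day, so at most 1 of 2 injections falls on an infusion day. On shared days Protocol 5.1 recommends injecting after the post-infusion observation period, whose length is not stated. At least half of the injections therefore fall on days when the infusion-reaction window cannot apply.

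6. **Where the event does appear.** SAP 5.8.1 plans all treatment-emergent events by system organ class and preferred term, and also by severity and by relationship to evinacumab. The event is counted there by treatment group.

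**The case against.** The strongest reply is that nothing is lost from the safety record. Site reactions remain visible by term and arm in the general tables, and SAP 5.8 makes all safety summaries descriptive. Separating site-limited from systemic terms is a defensible choice, since the risk named in Protocol 3.2.3 is systemic hypersensitivity. All of this stands. It limits the consequence but does not supply the missing class.

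Four stronger readings are tempting, and the documents do not support them.

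- *The allergic signal is understated.* Not shown. The SAP's allergic class has no consultation or treatment threshold, so in that respect it is wider than the protocol's AESI. The net direction is unknown.
- *Expedited reports will fail to reconcile with the study report.* This is conjecture. The SAP's query-based classes do not copy investigator-reported AESIs one for one.
- *The SAP hides a departure.* SAP 1.2.4 covers changes from the protocol's statistical section. The AESI lists are in the safety-reporting section, and 10.4.4.1 names only examples. The SAP also adds classes, such as immune complex diseases and muscle events, without entering them in 1.2.4.
- *The effect can be sized from the arm.* One of 38 evinacumab patients is 1/38 = 2.6%. That is the weight of one patient and not an estimate of how many are missed.

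**Conclusion.** The point holds as an inconsistency between protocol and SAP. A protocol-defined AESI component has no SAP class, and Table 3 excludes nine terms by reference to a category that the SAP does not contain. What is missing is the AESI display of these events; they remain in the general tables.

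The protocol's AESI is only the subset of local reactions that need consultation or, for evinacumab, medical treatment. The size of that subset cannot be estimated, because the documents give neither event rates nor the number of patients entering from R727-CL-1628. No primary, secondary or other inferential result is affected.

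The conclusion rests on two assumptions: that investigators tick infusion reactions according to the 2-hour definition in Protocol 9.3.4, and that the evinacumab wording on injection sites is meant to cover infusion sites. If sites tick later reactions as well, the gap is smaller for the infused drug, though it remains for alirocumab injections on days without an infusion.

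**What to change.** In SAP 4.8.1.2 and Table 3, add an AESI class for local infusion-site and injection-site reactions.

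- Define it by a term list that includes the nine terms now excluded from the general allergic class. The exclusion in that class can then stay, because the terms have a destination.
- Show it separately for IV study drug and for SC alirocumab. Protocol 9.4.3 defines the second list for alirocumab, not for every PCSK9 antibody.
- Within each, identify the events that meet the 9.4.3 threshold: consultation with another physician, or medical treatment in the case of evinacumab. The SAP should name the data source for this flag. The 24-hour AESI reports are one candidate.

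A single combined allergic line should not be added. Protocol 9.3.4 counts any adverse event in the window as an infusion reaction, so such a line would label non-allergic events as allergic.

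The cost is SAP wording, one term list and one additional descriptive entry. Adverse events are already coded in MedDRA (SAP 4.8.1.1), so the class itself needs no new data collection. No inferential result changes.

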10.4. Criteria for Potentially Clinically Significant Values (PCSV)

Parameter	PCSV
Clinical chemistry	
ALT	By distribution analysis: >2 ULN and baseline \leq 2 ULN >3 ULN and baseline \leq 3 ULN >5 ULN and baseline \leq 5 ULN >10 ULN and baseline \leq 10 ULN >20 ULN and baseline \leq 20 ULN
AST	By distribution analysis: >2 ULN and baseline \leq 2 ULN >3 ULN and baseline \leq 3 ULN >5 ULN and baseline \leq 5 ULN >10 ULN and baseline \leq 10 ULN >20 ULN and baseline \leq 20 ULN
Alkaline Phosphatase	> 1.5 ULN and baseline \leq 1.5 ULN
Total Bilirubin	> 1.5 ULN and baseline \leq 1.5 ULN > 2 ULN and baseline \leq 2 ULN
Conjugated bilirubin	> 35% total bilirubin (when total bilirubin >1.5 ULN)
ALT and Total Bilirubin	ALT > 3 ULN and Total Bilirubin > 2 ULN and baseline ALT \leq 3 ULN or Total bilirubin \leq 2 ULN
CPK	> 3 ULN and \leq 5 ULN and baseline \leq 3ULN >5 ULN and \leq 10 ULN and baseline \leq 5 ULN >10 ULN and baseline \leq 10 ULN
Creatinine	\geq 150 μ mol/L (adults) \geq 30% from baseline \geq 100% from baseline
CLcr (mL/min) (Estimated creatinine clearance based on the Cockcroft-Gault equation)	\geq 15 - <30 (severe decrease in GFR) \geq 30 - < 60 (moderate decrease in GFR) \geq 60 - <90 (mild decrease in GFR) \geq 90 (normal GFR)
eGFR (mL/min/1.73m ²) (Estimate of GFR based on an MDRD equation)	\geq 15 - <30 (severe decrease in GFR) \geq 30 - < 60 (moderate decrease in GFR) \geq 60 - <90 (mild decrease in GFR) \geq 90 (normal GFR)

Parameter	PCSV
Uric Acid Hyperuricemia: Hypouricemia:	>408 µmol/L <120 µmol/L
Blood Urea Nitrogen	≥17 mmol/L
Chloride	<80 mmol/L >115 mmol/L
Sodium	≤129 mmol/L ≥ 160 mmol/L
Potassium	< 3 mmol/L ≥ 5.5 mmol/L
Glucose Hypoglycaemia Hyperglycaemia	≤ 3.9 mmol/L and < LLN ≥ 7 mmol/L (fasted); ≥ 11.1 mmol/L (unfasted)
HbA1c	>8%
Albumin	≤25 g/L
Hs-CRP	> 2 ULN or >10 mg/L, if ULN not provided
Hematology	
WBC	< 3.0 Giga/L (3000/ mm ³) (Non-Black) < 2.0 Giga/L (2000/ mm ³) (Black) ≥16.0 Giga/L (16000/ mm ³)
Lymphocytes	>4.0 Giga/L
Neutrophils	< 1.5 Giga/L (1500/ mm ³) (Non-Black) < 1.0 Giga/L (1000/ mm ³) (Black)
Monocytes	>0.7 Giga/L
Eosinophils	> 0.5 Giga/L (500/ mm ³) or > ULN if ULN ≥ 0.5 Giga/L
Hemoglobin	≤115 g/L (Male); ≤95 g/L (Female) ≥185 g/L (Male); ≥165 g/L (Female) Decrease from Baseline ≥15 g/L Decrease from Baseline ≥20 g/L
Hematocrit	≤0.37 v/v (Male) ; ≤0.32 v/v (Female) ≥0.55 v/v (Male) ; ≥0.5 v/v (Female)
RBC	≥6 Tera/L

Parameter	PCSV
Platelets	< 100 Giga/L (100 000/mm ³) ≥700 Giga/L (700000/mm ³)
Urinalysis	

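### The SAP's hepatic AESI definition cannot give a per-arm count of the ALT/AST event that protocol section 9.4.3 defines

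*SAP*

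**What the plan says.** **Protocol.** Section 9.4.3, identical in both protocol versions, lists "Increase in ALT or AST" among the evinacumab AESIs that sites must report within 24 hours. The trigger is a value of at least "3 x ULN (if baseline <ULN), or" at least "2 times the baseline value (if baseline" at or above ULN). The alirocumab list has the same rule for ALT alone. Section 10.4.4.1 then plans incidence summaries of AESIs for each drug. The alirocumab line reads "All TEAEs of special interest for alirocumab treatment (ie, increase in ALT, etc".

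**SAP.** Section 4.8.1.2 carries a single entry, "Hepatic Disorder (SMQ, lab data". Table 3 in Appendix 10.3 spells it out as "SMQ Drug-related hepatic disorder", then "Potentially clinically significant value (PCSV) in Appendix 10.4", then Hy's law and the eDISH plot. Its e-CRF tick-box column says no. In Appendix 10.4 the ALT and AST criteria are five bands, at 2, 3, 5, 10 and 20 x ULN. Each requires the baseline to be at or below the same cut, for example ">3 ULN and baseline" at or below 3 ULN. Section 5.8.2 presents AESIs by system organ class and preferred term; the sources it names are the MedDRA queries and the e-CRF. The PCSV results are separate laboratory tables and listings under section 5.8.3.

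**The concern.** The protocol gives both a definition of the ALT/AST event and a plan to summarise AESIs. The SAP contains no multiple-of-baseline rule and no split of baseline at ULN, so its outputs cannot be read as counts of that event. By contrast, Table 3 does carry over the protocol's laboratory criteria for new-onset diabetes, so leaving this rule out is not a general policy of the SAP.

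The rules part mainly in patients who enter with raised enzymes. Eligibility excludes ALT or AST only above 3 x ULN at screening. Lomitapide and mipomersen, which the protocol's introduction links to liver-test increases, are permitted background drugs. What is at stake is whether the reported hepatic AESI figures can be reconciled, by arm, with the events that sites had to report quickly.

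**Working it through.** This is a comparison of definitions, so there is no planned figure to reproduce. Let b be baseline and v a post-baseline value, both in multiples of ULN.

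- Protocol 9.4.3: case if v >= 3 when b < 1, or v >= 2b when b >= 1.
- SAP Appendix 10.4, row k: flagged if v > k and b <= k, for k = 2, 3, 5, 10, 20.

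**1. By baseline range**

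- b < 1: the >3 row agrees with the protocol except at v exactly 3.0 (the protocol includes it, the row does not). The >2 row also takes in non-cases with v between 2 and 3.
- b from 1 to below 1.5: the protocol threshold 2b runs from 2 to below 3. The >3 row misses cases with v from 2b to 3, and the >2 row adds non-cases with v between 2 and 2b.
- b above 1.5 up to 3: the threshold runs from above 3 to 6. The >3 row adds non-cases with v between 3 and 2b.

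**2. Example patients**

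| b | v | Protocol threshold | Protocol AESI | PCSV rows |
|---|---|---|---|---|
| 0.8 | 2.5 | 3.0 | no | >2 |
| 1.2 | 2.5 | 2 x 1.2 = 2.4 | yes | >2 |
| 1.2 | 2.3 | 2.4 | no | >2 |
| 2.0 | 3.2 | 2 x 2.0 = 4.0 | no | >2, >3 |
| 2.5 | 4.9 | 2 x 2.5 = 5.0 | no | >3 |
| 2.5 | 5.0 | 5.0 | yes | >3 |
| 2.9 | 5.5 | 2 x 2.9 = 5.8 | no | >3, >5 |
| 2.9 | 5.9 | 5.8 | yes | >3, >5 |

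**3. Can the rows be combined to recover the protocol count?** No. Two patients with baseline 1.2, one reaching 2.5 and one 2.3, fall in exactly the same row, yet one is a case and the other is not. The two pairs at baselines 2.5 and 2.9 show the same. Counts by row therefore cannot separate cases from non-cases, whichever rows are added or subtracted.

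**4. Are protocol cases lost?** Almost none.

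- b < 1: v >= 3 puts the patient in the >2 row.
- b above 1 up to 2: v >= 2b > 2, so again the >2 row.
- b above 2 up to 3: v >= 2b > 4, so the >3 row.
- b = 1: any v above 2 is in the >2 row; only v exactly 2.0 is in none.

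A check on a 0.01 x ULN grid (b from 0.20 to 3.00, v from 0.50 to 10.00) finds that one point and no other.

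**5. Scale.** With the planned 38 and 19 patients, one reclassified patient moves a rate by 1/38 = 2.6% on evinacumab or 1/19 = 5.3% on placebo. How many would be reclassified depends on how many have a baseline of 1 to 3 x ULN and then a rise. The documents give neither number.

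**The case against.** The best defence is that little is lost in practice, and much of it stands.

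- A reader might infer that PCSV cut-offs have simply replaced the protocol rule. They have not: the MedDRA query comes first in Table 3, PCSV and Hy's law/eDISH stand beside it, and section 5.8.2 does not name PCSV as a source for the AESI table. The hepatic AESI rate is therefore not the >3 ULN row. The PCSV rows also do carry a baseline condition, though not the protocol's.
- A reader might infer that these events vanish from the report. They do not. Events that sites report under 9.4.3 are coded and appear in the treatment-emergent tables, and may reach the query-based AESI table; the documents do not show which coded terms that query captures. PCSV listings and a listing of possible Hy's law cases are also planned, so individual cases can be reviewed.
- A reader might infer that raised baselines will be common. The screening limit and the permitted background drugs make them possible, but the documents do not say how many patients take those drugs or what baseline enzymes look like.
- A reader might see an undeclared departure because SAP 1.2.4 is silent. That section covers changes from the protocol's statistical section, whereas the ALT/AST rule is in the safety-reporting section, so the silence is weak evidence.

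Finally, no safety testing is planned, and site reporting does not depend on the SAP. None of this supplies a table that applies the protocol rule by arm.

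**Conclusion.** The point holds in a limited form. The hepatic entry in SAP Table 3 cannot yield the AESI count by arm as protocol 9.4.3 defines it, although protocol 10.4.4.1 plans AESI summaries. For baselines of 1 to 3 x ULN the PCSV rows differ from the protocol rule in both directions. Cases are retained but mixed with non-cases.

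This rests on the text of the two rules and needs no assumption about how ALT or AST is distributed. The number of patients affected cannot be determined from the documents. In a trial of 57 it is likely small, since it takes both a raised baseline and a later rise, or a value exactly on a boundary. No endpoint or test depends on it. It is a protocol-SAP alignment point that should be corrected because the correction is cheap.

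**What to change.** Add to the Hepatic Disorders entry in SAP Table 3, and to the section 5.8.2 output, one laboratory-derived row per arm that applies the protocol's own 9.4.3 rule to ALT or AST during the treatment-emergent period. For the alirocumab summary, use ALT alone. State in 5.8.2 that this row comes from laboratory data, since the sources named there do not include it. Keep the MedDRA query, PCSV and eDISH displays as they are.

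The cost is one derived flag on central-laboratory data already being collected, and one table row. No clinical rule or site procedure changes.
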